- 1) Participant compliance: Participant compliance with the gait modification intervention will be measured by the number of training sessions attended at Fortius (to a maximum of 8, converted to a percentage) and the number of home training sessions completed (to a maximum of 22, converted to a percentage). Participants will record their home training sessions in their weekly online questionnaire.
- 2) Adverse events: Adverse events experienced due to the intervention (i.e. increased pain or a new injury) will be recorded in the weekly online questionnaires.
- 3) Fidelity of training sessions: Assessed by calculating the difference (error, in degrees) between the intended target angle and the actual angle produced during the 10 consecutive stance phases at each of the four time points during each training session (first min, 33%, 66%, and last min) and averaged within the session.
- 4) Perceived difficulty in achieving targeted modification: Assessed at each training session using an 11-point numerical rating scale (NRS) (0 = “no difficulty”, 10 = “unable to perform”).
- 5) Pain: Assessed at each training session using an 11-point NRS (0 = “no pain”, 10 = “worst pain imaginable”).
- 6) Rating of Perceived Exertion (RPE): Assessed at each training session using the 15-point Borg RPE scale.

- 7) Anthropometric and functional measurements: These will include BMI, navicular height, hip internal/external rotation range of motion, Q-angle, and weight-bearing ankle dorsiflexion and knee valgus angle.

Methods

The proposed study is a repeated measures design. A sample size calculation for comparing injury incidence is based on our current injury rate (27.9%) in our previous studies. We calculate that we will require a sample size of 30 to achieve a minimum power of 80% ($\alpha = 0.05$). Thirty uninjured female recreational runners will be recruited through advertisements in Vancouver-area running clinics. Participants must be female between the ages of 18 and 60; have been running for at least three months prior to study commencement; and have experience with running on a treadmill. Participants must not have run more than two half marathons previously. Participants will be excluded if they have experienced a lower extremity injury in the prior three months; have undergone hip, knee, or ankle joint surgery; or currently have pain in their lower back or lower extremities while running.

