Participants will follow a 15-week half-marathon training program, wearing their regular running shoes throughout the study. During the training program, participants will attend the Fortius Biomechanics Lab on Weeks 1, 2, 4, 6, 8, 10, 12, and 14 (eight sessions in total) for a 15-30 minute gait modification training session following a faded-feedback design (figure 1)[1]. The aim of these sessions will be to modify the angle of knee flexion at IC so that it is greater than 10 degrees. Gait modification will be facilitated through the use of real-time biofeedback of performance[1,24,25] at each training session. The co-investigator, a sport physiotherapist, will also provide standardized verbal instructions to change the desired biomechanical outcome (e.g. “Land with a more bent knee”). For the first four sessions, participants will receive feedback for 100% of the session. By the eighth session, feedback will be provided for just 10% of the session (minutes 1, 15, and 30). All participants will have a total of 60 running sessions (four times per week for 15 weeks). During the weeks in which a lab-based gait modification session is scheduled, participants will have one lab-based biofeedback session and three “regularly scheduled” run sessions in which they will be instructed to focus on the same cues given in the lab during their runs. During the weeks in which no lab-based feedback session is scheduled,

participants will only have the four “regularly scheduled” run sessions in which they will be instructed to focus on the same cues given in the lab during their runs. This will ensure that they do not have any more run sessions than the historical control group.

Figure 1. Faded-feedback design depicting time spent running on the treadmill during each session and time with visual real-time biofeedback for each session. For the first four sessions, participants will receive feedback for 100% of the session. By the eighth session, feedback will be provided for just 10% of the session.

Kinetic, kinematic, and spatiotemporal data will be collected during each session to ensure that the goal of the intervention is being achieved. This will be assessed by calculating the difference (error, in degrees) between the intended target angle and the actual angle produced during the 10 consecutive stance phases at each of four time points during each training session (first min, 33%, 66%, and last min) and averaged within the

session.

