Pain, RPE, and perceived difficulty in achieving the targeted modification will be measured in all training sessions using an 11-point NRS (pain and perceived difficulty) and the Borg RPE scale. Adverse events (increased pain or a new injury) and participant compliance with the gait intervention will be assessed in the weekly online questionnaire.

All participants will return to the Fortius Biomechanics Lab at the conclusion of the 15-week half-marathon clinic for retesting. A one-month post-test will also be performed to assess for retention. During both sessions (follow-up and retention), the participants will be asked to run naturally and then with the modified pattern. The natural pattern will be collected to determine whether it has changed since baseline.

The verbal instruction during each training session will be given by the principal investigator (a sport physiotherapist with clinical experience in gait retraining). The therapist will not be involved in data collection, but will process the data. To ensure blinding, data will be collected by an independent lab assistant and coded to blind for participant number for later processing and analysis by the principal investigator. This process will ensure that the principal investigator is unaware of which participant they are analyzing until the conclusion of the study.

Demographic, anthropometric, and functional variables will be analyzed for differences between the intervention group and a historical control group from our previous studies at baseline using 2-tailed t-tests for normally distributed continuous variables. Injury incidence (number of new injuries reported per 100 runners at risk) will be compared between groups using paired t-tests. Differences in outcomes pertaining to the feasibility of the intervention (perceived difficulty, exertion, fidelity, compliance) will

be assessed in the intervention group between session 1 and 8 using paired t-tests. The biomechanical and clinical outcomes from the follow-up and one-month post-intervention modified patterns will be compared to the baseline values using ANOVAs for repeated measures. Planned pairwise comparisons between the visits will be conducted. Differences will be considered statistically significant at $p < 0.05$. All statistical analyses will be performed using SPSS version 22.0 (SPSS Inc., Chicago, IL).

References

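### Session-8 fidelity averages two windows with feedback and two without, so the session 1 versus 8 test mixes learning with withdrawal of feedback

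*Combined protocol and SAP*

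**What the plan says.** All references are to the combined protocol and SAP.

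- **Feedback schedule (Methods, gait modification sessions).** Participants attend eight lab visits, each "for a 15-30 minute gait modification training session following a faded-feedback design". At the start of training, "For the first four sessions, participants will receive feedback for 100% of the session". By session 8, "feedback will be provided for just 10% of the session (minutes 1, 15, and 30".
- **Fidelity measure (Other outcome measures, item 3, repeated in Methods).** The outcome is called "Fidelity of training sessions". It is "Assessed by calculating the difference (error, in degrees) between the intended target angle and the actual angle produced during the 10 consecutive stance phases", taken at "four time points during each training session (first min, 33%, 66%, and last min) and averaged within the session". Whether the error is signed or absolute is not stated.
- **Analysis (Methods, statistical paragraph).** Fidelity is one of the feasibility outcomes, which will "be assessed in the intervention group between session 1 and 8 using paired t-tests".

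The text does not separate windows with feedback from windows without it, either in the definition or in the test.

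**The concern.** Fading exists so that runners learn to hold the target without being shown it. The Background says so: once feedback is removed, runners must rely on internal cues. Most of the program also takes place away from the lab. Of 60 planned runs, eight are lab sessions, and for the others the plan describes remembered cues but no biofeedback. A reader will naturally take session-8 fidelity as evidence on whether the modification holds once feedback is nearly gone.

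The sampling windows do not line up with that use. Two of the four coincide with feedback minutes, and the average gives them half the weight. Session 1 has feedback throughout, so the test compares a value obtained fully with feedback with one that is half and half. A change could reflect learning, loss of feedback, or both. No change could mean that neither occurred or that the two cancelled. At stake is the interpretability of one feasibility test.

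**Working it through.** **Inputs, all from the plan.** Session-8 feedback minutes: 1, 15 and 30. Stated feedback share: 10%. Session length: 15 to 30 minutes. Session-1 feedback: 100%. Fidelity windows: first minute, 33%, 66%, last minute.

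**Step 1: reproduce the stated share.** 3 min / 30 min = 10%, as the plan says. Because minute 30 is used and 30 is the longest session allowed, session 8 lasts 30 minutes.

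**Step 2: place the windows.**

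| Window | Time in a 30-min session | Session 8 | Session 1 |
|---|---|---|---|
| First minute | minute 1 | on | on |
| 33% | 0.33 × 30 = 9.9 min | off | on |
| 66% | 0.66 × 30 = 19.8 min | off | on |
| Last minute | minute 30 | on | on |

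The session-1 column holds for any session length, because feedback is continuous. The off entries do not depend on how a one-minute window is set around its nominal time. Whether it starts, ends or is centred there, it stays within 8.9 to 10.9 min or 18.8 to 20.8 min, clear of minute 15.

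**Step 3: weight.** In session 8, 2/4 = 50% of the average comes from feedback minutes, against 10% of session time: 50/10 = 5 times over-represented.

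**Step 4: effect on the session-8 value.** Let e_on and e_off be the session-8 errors with and without feedback.

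- Planned average: (2·e_on + 2·e_off)/4 = e_off − (e_off − e_on)/2.
- Time-weighted value: 0.1·e_on + 0.9·e_off.

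The planned average therefore removes exactly half of any on/off difference. The documents give neither error, so the degrees below are assumptions that show the range only.

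| e_on (°) | e_off (°) | Planned average (°) | Time-weighted (°) | e_off minus planned average (°) |
|---|---|---|---|---|
| 2 | 2 | 2.0 | 2.0 | 0 |
| 2 | 3 | 2.5 | 2.9 | 0.5 |
| 2 | 4 | 3.0 | 3.8 | 1.0 |
| 2 | 6 | 4.0 | 5.6 | 2.0 |
| 3 | 2 | 2.5 | 2.1 | −0.5 |

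The gap is zero if feedback makes no difference and reverses if feedback worsens the error.

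**Step 5: what the planned test estimates.** Let A1 and A8 be the mean error over the first and last minutes in sessions 1 and 8, and B1 and B8 the mean over the 33% and 66% windows. The planned difference is

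(A8 + B8)/2 − (A1 + B1)/2 = ½(A8 − A1) + ½(B8 − B1).

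A8 − A1 has feedback on in both sessions. B8 − B1 goes from feedback on to feedback off. The test reports only their average, so equal and opposite changes would give zero.

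**The case against.** The strongest reply is that the plan never promises a measure of performance without feedback. The outcome is fidelity of the sessions, listed under other outcomes and analysed for feasibility, and the stated aim of the sessions is a knee angle above 10 degrees. Faulting the average for not measuring unaided running holds it to a quantity the plan does not name. This stands, and it limits the point. But it does not rescue the average as a whole-session summary, because 50% weight for 10% of the time does not represent the session either.

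A second reply is that lasting change is tested elsewhere. The follow-up and one-month visits record natural and modified running, the modified patterns are compared with baseline, and knee flexion at initial contact is a secondary outcome. This also stands. A reader might infer that the mixed average undermines any explanation of the AVLR result; the documents do not support that, since those visits bear on the question more directly.

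A third reply concerns direction. A reader might infer that the overlap makes session-8 fidelity look too good. That requires error to be smaller with feedback, which is plausible given why biofeedback is used, but the documents give no data. If the error is signed, the direction is undetermined. Even where feedback does help, session 1 has it in four windows and session 8 in two, so the comparison already tends to disfavour session 8. The overlap would hide part of a loss; it would not by itself put session 8 ahead of session 1.

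Finally, taking only the 33% and 66% windows from session 8 and all four from session 1 would be a poor repair, because it would mix feedback status with time in session (settling in, fatigue). That is correct, and it is why the windows should be matched.

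**Conclusion.** The point holds as a matter of timing and weighting. Two of the four session-8 windows are feedback minutes, giving 50% weight to 10% of the session, while all four session-1 windows have feedback. The session 1 versus 8 test is an equal mix of a contrast with feedback in both sessions and a contrast in which feedback is withdrawn. The session-8 average removes half of any on/off difference.

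This rests on session 8 lasting 30 minutes, which the plan's own minutes and percentage imply. The effect in degrees cannot be stated, and neither bias in a known direction nor any consequence for the primary outcomes is established. Sessions 5 to 7 cannot be assessed from the text, because the figure showing their feedback times is not available here. It is a cheap improvement to the interpretability of a feasibility outcome.

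**What to change.** 1. Report session-8 fidelity error separately for the feedback-on windows (first and last minute) and the feedback-off windows (33% and 66%).
2. Replace the single session 1 versus 8 test by two paired contrasts on matched windows:
   - first and last minute, with feedback on in both sessions, which shows learning;
   - 33% and 66%, with feedback on in session 1 and off in session 8, which shows performance once feedback is withdrawn.
3. Pre-specify which contrast is the main one.
4. State whether the error is signed or absolute.

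Matching is by relative position in the session. If session 1 is shorter than 30 minutes, the 33% and 66% points fall at earlier clock times than in session 8, which should be noted when the second contrast is read.

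The change is to wording only, since the plan already records every window. The downside is that each contrast rests on two windows instead of four, so it will be less precise, and there are two contrasts where there was one. Naming the main contrast in advance deals with the latter.

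### Injury, itself a primary outcome, can make the post-training AVLR and impact-peak values missing or altered, and the plan neither records injury at the retests nor says how such values are analysed

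*Combined protocol and SAP*

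**What the plan says.** The Outcome Measures section lists AVLR and vertical impact peak as the first primary outcome and incidence of running-related injury as the second.

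Under Methods, the sample-size sentence reads "A sample size calculation for comparing injury incidence is based on our current injury rate (27.9%) in our previous studies". Recruitment is described as "Thirty uninjured female recreational runners will be recruited through advertisements in Vancouver-area running clinics". Runners are excluded if they had a lower-extremity injury in the previous three months or if they "currently have pain in their lower back or lower extremities while running". Baseline loading is therefore measured in uninjured, pain-free runners.

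The retesting paragraph in Methods states "All participants will return to the Fortius Biomechanics Lab at the conclusion of the 15-week half-marathon clinic for retesting" and adds a retention test one month later. The statistical paragraph compares modified-pattern values at these two tests with baseline by repeated-measures ANOVA.

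New injury and increased pain are collected by weekly online questionnaire, and pain is scored at every training session. For those sessions the plan also says "Kinetic, kinematic, and spatiotemporal data will be collected during each session", to check that the target angle is being reached. The documents contain no missing-data rule, analysis set, dropout allowance or sensitivity analysis. They do not say how AVLR is handled when a runner is injured, runs in pain or misses a retest.

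**The concern.** One primary outcome can decide whether the other is measurable, and what it means when it is measured. There are two routes.

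- **Not testable.** A runner too injured to run has no post-training value. A standard repeated-measures ANOVA then loses her entirely, even if she attended the other retest. The result describes runners still able to run, not the 30 who were trained.
- **Tested hurt.** A runner who completes the test with a current injury gives an observed value. If she has changed her gait because of the injury, the analysis attributes that change to training. No missing-data method repairs this, because nothing is missing. Test speed is set by perceived exertion (RPE 13), so an injured runner may also be tested at a different speed, which is another way for injury to reach AVLR.

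The within-group change in AVLR could therefore be partly a product of injury, and a reader could not tell how much. If the handling is chosen after the data are seen, the choice is open to the results.

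**Working it through.** **Inputs from the documents.** 30 runners; injury rate 27.9%; tests at baseline, week 15 and one month later; lab sessions in weeks 1, 2, 4, 6, 8, 10, 12 and 14, with feedback throughout the first four.

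**The plan's own figure.** The stated 30 for 80% power cannot be reproduced, because no intervention-group injury rate is given. Only the 27.9% is used below.

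**Step 1: runners injured at some time.** 30 × 0.279 = 8.37, about 8. The 2.5% and 97.5% points of a binomial(30, 0.279) are 4 and 13. This assumes that training prevents no injury and that the rate counts runners over a comparable period; the plan states neither. At half the rate the expected number is 4.2, and the chance of at least one is 1 − (1 − 0.1395)^30 = 99%.

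**Step 2: runners who cannot be tested.** Assumptions, not in the documents: AVLR change is standard normal in SD units; injury follows a logistic model calibrated to 27.9%, with odds 1.5, 2 or 3 times higher per SD of smaller AVLR reduction; a fraction f of the injured, chosen at random, is untestable. Let m be the shift in mean change among the uninjured. The shift among those tested is then f(1 − 0.279)m / (1 − 0.279f). Numerical integration gives m = 0.11, 0.18 and 0.25 SD. The standard error (SE) is 1/√n SD.

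| Share of injured untestable | Expected n tested | Shift in SD (odds ratio 1.5, 2, 3) | Shift in SE |
|---|---|---|---|
| 25% | 27.9 | 0.02, 0.03, 0.05 | 0.1 to 0.3 |
| 50% | 25.8 | 0.05, 0.07, 0.11 | 0.2 to 0.5 |
| 100% | 21.6 | 0.11, 0.18, 0.25 | 0.5 to 1.2 |

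Example for f = 0.5 and odds ratio 1.5: 0.5 × 0.721 × 0.11 / 0.8605 = 0.05.

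**Step 3: runners tested hurt.** Shift = 0.279 × share tested hurt × assumed shift in those runners. Half tested hurt with a 0.5 SD shift: 0.279 × 0.5 × 0.5 = 0.07 SD. All tested hurt with a 1 SD shift: 0.279 SD. With SE = 1/√30 = 0.183 SD, these are 0.4 and 1.5 SE.

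**Step 4: loss of precision.** For a two-sided paired t-test at 0.05, 30 runners give 80% power for a standardised change of 0.53. At that change, power is 74% with 26 runners and 66% with 22.

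**Step 5: can session data fill the gap?** If injuries are spread evenly over 15 weeks, about 7/15 (47%) fall before week 8, the first session at which feedback could be less than full. Those runners have at most feedback-on values before injury. Sessions record 10 stance phases at each of four time points with no stated speed rule; the tests use three 15-second trials at RPE 13. Session AVLR is not shown to be comparable with test AVLR.

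**The case against.** The strongest reply is that 27.9% is a rate of injury at any time, from previous studies, with no stated time window. The outcome counts new injuries, so one runner may count twice. Many injured runners may have recovered by week 15. The plan also hypothesises fewer injuries: read as 30 per group, 80% power needs an intervention rate between 0% and about 5%, which leaves only 0 or 1 injured runners. All of this stands, and it is why the table starts at a quarter of the injured. It limits the size of the problem. It does not remove the need for a rule, because the plan must also give a readable result if training does not prevent injury.

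A reader might infer that the AVLR reduction must be exaggerated. The documents do not support that. The Objectives tie knee angle at contact to both AVLR and injury; they do not say that a smaller AVLR change predicts injury. The Background warns that changing gait may raise the chance of a different injury. On that mechanism the runners who changed most could be lost, and the reduction would be understated. Nor do the documents say that running hurt lowers loading.

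It can also be said that injury is largely captured already, by weekly questionnaire and by pain scores up to the week 14 session, and that the statistical paragraph mentions clinical outcomes at the retests. That is partly right. Those clinical outcomes are not defined, however, and nothing links the injury records to the AVLR analysis.

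Finally, analysing everyone as tested is a legitimate target and fits the instruction to retest all participants. This stands, and the fix keeps it as the main analysis.

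**Conclusion.** The point holds as a gap in measurement and analysis with an unknown net direction. Followed as written, with the standard repeated-measures procedure, the plan drops incompletely tested runners and treats values recorded while hurt as training effect.

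The documents support about 8 of 30 runners injured at some time, if the previous-study rate applies and training prevents none. They do not support reading this as 8 runners unable to be tested, or tested hurt, at week 15. On the stated assumptions the effect runs from negligible (0.02 SD) to more than one standard error (0.25 to 0.28 SD). The upper end requires every injured runner to be affected at the test. The odds ratios, gait shifts and shares affected are assumptions; only the 27.9% and the 30 come from the plan. The change should be made because it is cheap and must be settled before the data are seen.

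**What to change.** In the retesting and statistical paragraphs of Methods:

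1. Record current injury status and the 0–10 pain score at the follow-up and one-month tests.
2. Replace the repeated-measures ANOVA for AVLR and impact peak with a mixed model of baseline, follow-up and one-month values. Keep every runner with any post-baseline test, and take all values as tested as the main analysis.
3. Pre-specify a sensitivity analysis that leaves out values recorded during a current injury. Report the number injured and the number untested at each visit.
4. Tabulate AVLR at the last pre-injury lab session for injured and uninjured runners. Label it supportive only, because session values are taken partly or wholly with biofeedback on and under a different measurement protocol.

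The mixed model relies on missing values being explained by the observed ones. A runner with only a baseline value still tells nothing about change, which is why the counts in item 3 are needed. The cost is a brief injury and pain question at two existing visits and a little more analysis, with no extra visits or participants.

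### The stated blinding covers participant number only; the plan does not say that visit or gait condition is masked, and these are what separate the two sides of every within-runner biomechanical comparison

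*Combined protocol and SAP*

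**What the plan says.** All references are to the Combined protocol and SAP.

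- **Who treats and who processes.** The blinding paragraph in Methods states that "The verbal instruction during each training session will be given by the principal investigator". It continues: "The therapist will not be involved in data collection, but will process the data".
- **What is masked.** An independent lab assistant collects the data, which are "coded to blind for participant number for later processing and analysis by the principal investigator". The stated result is: "This process will ensure that the principal investigator is unaware of which participant they are analyzing until the conclusion of the study". Visit, gait condition and processing order are not mentioned there or elsewhere.
- **What is compared.** The analysis paragraph at the end of Methods says that follow-up and "one-month post-intervention modified patterns will be compared to the baseline values using ANOVAs for repeated measures", with planned pairwise comparisons between visits. The retesting paragraph adds that both natural and modified running are recorded at each post-test, the natural pattern being kept to see whether it has moved from baseline.
- **A conflicting statement.** The paragraph on the training sessions gives the instruction to a different role: "The co-investigator, a sport physiotherapist, will also provide standardized verbal instructions".

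**The concern.** Masking protects a comparison only if it hides what distinguishes the two sides. Here both sides come from the same runner, so hiding the runner's number does little. A processor who knows that one file is baseline and another is post-training has what is needed to treat them differently, knowingly or not, whether or not the runner is identified.

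Two features make this worth raising. By the blinding paragraph, the processor is also the person delivering the intervention. And no concurrent control recordings enter the repeated-measures analysis: the historical controls are named for the baseline and injury comparisons only. A processing shift tied to visit would therefore not cancel out. At stake are vertical impact peak, which is a primary outcome, and the knee and shank angles, which are secondary.

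**Working it through.** The plan gives no figure for this point, so the check sets the text side by side.

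**Step 1. Which label separates the sides of each comparison?** The inputs are the retesting and analysis paragraphs of Methods, the entry criterion (under 10° of knee flexion at initial contact) and the training target (over 10°).

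| Comparison | Status in the plan | Separated by | Would the knee angle reveal the side? |
|---|---|---|---|
| Baseline v modified gait at follow-up | Repeated-measures ANOVA | Visit and condition | Probably, where the target is met |
| Baseline v modified gait at one month | Repeated-measures ANOVA | Visit and condition | Probably, where the target is met |
| Modified gait, follow-up v one month | Planned pairwise comparison | Visit | Not by design |
| Baseline v natural gait at either post-test | Data collected; no test named | Visit | Only if the natural pattern has itself changed |

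Participant number separates the sides in none of the four rows.

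**Step 2. How much judgement does processing leave?** The input is the data-collection part of Methods.

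- *All outcomes:* initial contact and toe-off come from a 50 N force threshold. Values are averaged over the opening run of ten stances in each of three trials (10 × 3 = 30 stances).
- *AVLR:* the gradient of vertical force between initial contact and 13% of stance, for every runner. This uses force-plate data only. With the threshold and stance rule above, little is left to choose.
- *Vertical impact peak:* the plan recognises that midfoot and forefoot strikers may show no clear peak. The 13% rule is given for AVLR. No rule says what value the peak takes when it is absent.
- *Knee and shank angles:* these rest on the marker system and segment model (19 + 42 = 61 markers). No marker-processing or filtering rules are stated.
- *Exclusions:* no rule says when a trial or stance is unusable. An exclusion could alter any of the outcomes, including AVLR.

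**Step 3. How many files would the fuller code cover?** There is one baseline recording, two at follow-up and two at one month: 1 + 2 + 2 = 5 per runner. With 30 runners and no dropout, 5 × 30 = 150 sets. If the retests repeat the three-trial procedure described for baseline testing (an assumption), that is 150 × 3 = 450 trials.

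**Step 4. Can the bias be sized?** No. The documents contain no repeat-processing error, no between-processor difference and no standard deviation for these outcomes. Any assumed shift could be turned into a false-positive rate, but the shift would have no source in the plan.

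**The case against.** The strongest reply has four parts.

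1. *The plan is silent; it does not say that labels are visible.* This stands. A reader might infer that the processor will see which visit each file belongs to. The text does not say so. What it supports is that masking of visit and condition is not stated, although the plan presents its procedure as ensuring blinding.
2. *Fixed rules leave little to bias.* This stands for AVLR. A reader might infer that marker labelling or model building feeds into loading rate; as defined, it does not. The reply does not reach an absent vertical impact peak, the joint and segment angles, or exclusions.
3. *Recoding does little for the main contrast.* This stands in part. A runner who enters below 10° and meets a target above 10° reveals the condition through the knee angle itself. Follow-up against one month, and natural gait against baseline, would still benefit. Where files can be recognised, rules fixed in advance are the remaining protection.
4. *Some data must be processed during the study.* This stands. Eligibility depends on knee angle, and each training session is monitored against the target. A fix that delayed all processing to the end would not be workable.

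**Conclusion.** The point holds in a limited form. The stated mask does not cover what separates the two sides of the within-runner comparisons, and the plan does not state that visit or condition is hidden from the investigator who processes the data. AVLR is largely protected. The exposure lies in vertical impact peak without a clear peak, knee and shank angles, and unstated exclusions.

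Two stronger conclusions may tempt a reader and are not supported. One is that the error rate is inflated by a known amount: the size cannot be derived from the documents, and nothing shows that bias will occur. The other is that both primary outcomes are compromised: injury incidence counts reported injuries and does not pass through motion or force processing.

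That the processor also treats rests on the blinding paragraph. If the training-session paragraph is correct instead, the overlap of roles would need to be re-examined, but the gap in masking remains.

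**What to change.** Amend the blinding paragraph in Methods as follows.

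- The independent lab assistant, already in place, codes every baseline, follow-up and one-month outcome file for participant, visit and gait condition, and supplies the files in random order.
- Before outcome processing starts, write down the rules for marker processing, for excluding trials or stances, and for vertical impact peak when no clear peak is present.
- Release the key only after processing and exclusions are locked.
- Keep eligibility screening of knee angle and session-by-session monitoring separate from this blinded outcome processing. State whether screening recordings also serve as baseline; if they do, process them again under code with the rest.
- Acknowledge that modified-gait files may be recognisable from the angle, so the gain is greatest for natural-gait and follow-up versus one-month comparisons.

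Separately, reconcile the two Methods paragraphs on whether the co-investigator or the principal investigator gives the verbal instruction.

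The cost is a short amendment, a written set of processing rules and a fuller file code for about 150 sets of recordings. No new staff are needed. The drawback is that outcome processing must wait for the last one-month visit or be done in mixed batches.
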